1.0 Objectives

Primary objective:

1. To evaluate the complete response (CR) rate with SGI-110 in patients with higher risk myelodysplastic syndrome (MDS).

Secondary objectives:

1. Overall response rate, survival, transformation to AML, transfusion independence
2. Safety and toxicity

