2.0 Background

2.1 Myelodysplastic syndromes (MDS)

MDS is a heterogeneous group of hematopoietic stem cell disorders characterized by dysplastic changes in myeloid, erythroid, and megakaryocytic progenitors, and associated with cytopenias affecting one or more of the three lineages (1-4). Patients often present with complications related to anemia (fatigue), neutropenia (infections), or thrombocytopenia (bleeding). In addition, variable blast expansion and, less commonly, leukocytosis are observed. MDS may evolve into acute myeloid leukemia (AML) in 10% to 70% of patients.

The French-American-British (FAB) classification system recognizes four distinct subtypes of MDS, in addition to chronic myelomonocytic leukemia (CMM), based on morphology and percentage of marrow blasts: RA, RARS, RAEB, RAEB-t. Prognosis of MDS patients is poor. Patients die either from complications associated with cytopenias (infections and bleeding) or transformation to AML. In practice, "low-risk" MDS may be distinguished from "high-risk" MDS by the degree of pre-leukemic blast expansion together with the combination of cytogenetic changes and degree of cytopenia. These factors have allowed the establishment of an International Prognostic Scoring System (IPSS) to predict survival and progression to AML (5).

Table 1. IPSS for MDS - Model

Variable	0	0.5	Score	1.0	1.5	2.0
BM blasts (%)	< 5	5-10	-	11-20	21-30	
Karyotype *	Good	Intermediate	Poor			
Cytopenias	0/1	2/3				

Score for risk groups: Low, 0; INT-1, 0.5-1.0; INT-2, 1.5-2.0; High > 2.0

* Good, normal, -Y, del(5q), del(20q); poor; complex >= 3 abnormalities, or chromosome 7 abnormalities; intermediate, other abnormalities.

Based on this scoring system, patients with low-or intermediate-1 risk MDS (approximately 70% of patients) have an expected median survival of 3.5 to 5.7 years. Median survival for patients with intermediate-2 and high-risk MDS ranges from 0.4 - 1.2 years.

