2.2 The Treatment – Hypomethylating agents or “epigenetic therapy”

The standard for MDS therapy for many years has been supportive care (2,4). With the exception for allogeneic transplant, no modality has been shown to affect the outcome of patients with MDS. Intensive chemotherapy was associated with CR rates of 40% to 60%, induction mortality rates of 10% to 40% and no improvement in survival (4). The introduction of hypomethylating agents has changed the outlook of therapy for MDS. Azacitidine was given to 99 patients with MDS and compared with observation (n=92); 67% had advanced-stage disease by FAB. The response rate on the treatment arm was 60%: 7% CR and 16% PR, 37% HI. This was compared to 7% HI with observation ($p<.001$). The median time to leukemic transformation or death was 21 months on treatment and 13 months on observation ($p=.007$). Median survival was 20 months for azacitidine and 14 months for the control ($p=.1$). Quality of life measures were higher for azacitidine. Azacitidine was relatively well tolerated, although side effects included cytopenias and one treatment-related death. The results of this study led to approval of azacitidine in MDS and confirmed a role for hypomethylating agents in this disease (6). Similar data were noted with a second randomized study of azacitidine versus conventional care in Europe (7).

Decitabine is a deoxycytidine analog, which is phosphorylated to its nucleotide and incorporated into DNA. Once incorporated, it covalently binds to DNA-methyltransferases and traps the enzyme thus acting as an irreversible inhibitor of DNA-methyltransferase. Decitabine produces marked DNA hypomethylation (superior to azacitidine in this effect) via inhibition of DNA methyltransferase (8). At high doses, decitabine appears to cause DNA synthesis arrest due to the formation of a DNA/DNA- methyltransferase adduct, which results in cytotoxicity and apoptosis. At low doses, minimal cytotoxicity is observed, and treated cells exhibit marked reduction in DNA-methyltransferase activity, reduced overall and gene-specific DNA methylation and reactivation of silenced genes. This is associated with tumor suppressor gene activation, induction of cellular differentiation, and inhibition of clonogenic growth of leukemic progenitors.

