Based on in-vitro data suggesting greater hypomethylating activity at lower doses, a phase 1 biological study of decitabine was initiated at MD Anderson. To maximize the hypomethylating effects of decitabine, multiple low dose schedules in patients with relapsed/refractory myeloid malignancies were tried. Initially, patients were treated at 5 mg/m² iv over 1 hour daily for 10 days (dose 30-fold lower than the reported MTD). The dose was then escalated to 10, 15, and 20 mg/m² daily for 10 days. Finally, a group of patients received 15 mg/m² daily for 15 days then 20 days. A total of 48 patients were enrolled on the study. Responses were seen at all dose levels, but 15 mg/m² appeared to induce the most responses, with no further benefit for increasing the dose or duration of administration. There were 9 complete remissions (CR 18%) and 7 partial remissions (14%), for a response rate of 32%. Responses were seen in refractory/relapsed AML (8/37 = 22%), MDS (4/7 = 57%), and CML (4/5 = 80%). In some patients who responded, there was a gradual diminution of blasts over 2-4 weeks, and eventual recovery of normal hematopoiesis at 5-6 weeks, suggesting a non-cytotoxic mode of action for this regimen. Response duration ranged from 2 months to 10+ months. Therefore low-dose decitabine was established as effective in myeloid malignancies, and appeared to induce remissions in part through epigenetic modulation rather than cytotoxicity.

Wijermans et al. updated the results of 169 patients with MDS treated on multiple studies with decitabine 45-50 mg/m² iv (continuous infusion, or over 4 hours q 8 hours) daily x 3 (135-150 mg/m² per course) every 4-8 weeks (8). The CR rate was 20%, the overall response rate was 50%, the induction mortality was 8%. The median response duration was 9 months; the median survival was 15 months. There was no difference in response rate by risk group (Table 2)

Table 2. Decitabine - response rate in MDS by risk group

IPSS Risk Group	% Response	Median Response Duration (mos)	Median Survival (mos)/% 2-yr.
Intermediate-1	46	13	23/49
Intermediate-2	52	9	15/25
High	51	8	12/26

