2.4 Rationale for Proposed Schedule

The best approach for patients with higher-risk MDS remains to be defined. Both azacitidine and decitabine by themselves have low objective response rates, and a modest and limited survival benefit. From the early phase 1-2 experiences with SGI-110, it appears to be potentially more effective and perhaps safer than azacitidine and decitabine. We would like to expand our institutional experience with SGI-110 in newly diagnosed higher risk MDS to define more precisely the rates of CR, overall response, duration of response, survival and toxicity profiles. We will also assess determinants of better outcome with SGI-110 in MDS. The schedule chosen is based on the Phase II expansion of SGI-110 in higher risk MDS which treated a limited number of 40 patients. We will use SGI-110 60mg/m² subcutaneously daily x 5 every 4 weeks. We would like to gain experience on the efficacy, outcome and safety in 100 patients with newly diagnosed MDS. The primary endpoint of the study is the objective CR rate. Secondary endpoints are overall response rate, rates of survival and transformation to AML, and toxicity profile.

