6.0 Evaluation during Study

- CBC with differential and platelet counts weekly in the first course, then every 2 to 8 weeks thereafter as long as on study. No differential is needed if the WBC is $< 1.0 \times 10^9/L$.
- Chemistry profile (at least creatinine, SGOT or SGPT, total bilirubin) every 2-8 weeks while on therapy, then every 8 to 12 weeks as long as on study.
- Bone marrow aspirate and/or biopsy at the end of course 1 and/or 2 of SGI-110 (day 28 +/- 7 days). If a patient is not in remission at this point, further bone marrow aspirate and/or biopsy should be scheduled to document remission, for example at the end of course 6 (day 28 +/- 7 days).
- Bone marrow tests can be ordered more frequently if mandated by development of peripheral blood counts. No repeat bone marrow is necessary if non-response or progressive disease can be unequivocally diagnosed from peripheral blood tests or, in patients with a WBC ≤ 0.3 if the bone marrow test is considered non-contributory by the investigator at any time point.
- Follow up marrow tests should include cytogenetic analysis for those patients who had abnormalities prior to therapy start.
- Repeat physical examination (problem focused) on Day 1 (± 3 days) of every cycle as long as on active therapy.
- After completion of therapy and/or 30 days after last dose of study drug, patients will be observed for survival only when off active treatment. Patients will be called 30 days after last dose of study drug and every 2 months ($+- 2$ months) thereafter.
- Optional: Blood 10cc pretreatment and on Day 5 $+- 2$ days and Day 14 $+- 2$ days to evaluate effect of SGI-110.
- All outside labs will need to be reviewed, signed and dated by the Principal Investigator (PI) or treating physician (listed on the Delegation of Authority) prior to submission to the electronic medical record. The PI or treating physician should appraise abnormal lab results and determine/document clinical significance

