The number of patients evaluated for mortality	5	10	15	20	25	30	35	40	45	50	55	60	65	70	75	80	85	90	95
The number of patients dead is greater than or equal to	3	4	5	5	6	7	8	8	9	10	10	11	12	12	13	14	14	15	15

Table 8. Operating characteristics for mortality monitoring

True Mortality Rate	Early Stopping Probability	Sample Size		
		25 th percentile	Median	75 th percentile
0.06	0.0111	100	100	100
0.08	0.0444	100	100	100
0.10	0.1291	100	100	100
0.12	0.2751	85	100	100
0.14	0.4759	40	100	100

Statistical Analysis Plan

All patients who received at least 1 dose of the experimental treatment will be included in the intent-to-treat analysis for efficacy and safety. Safety data will be summarized using frequency and percentage, by organ type, grade and attribution. Complete response and overall response rates will be estimated along with the 95% credible intervals. Survival times (overall survival, time to AML transformation and event-free survival) will be estimated using the Kaplan-Meier method for each patient cohort.

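### Kaplan-Meier is the only method planned for time to AML transformation, with no event definition and no rule for death without AML

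*Combined protocol and SAP*

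**What the plan says.** Section 9.0, under the Statistical Analysis Plan, gives one sentence on time-to-event endpoints: "Survival times (overall survival, time to AML transformation and event-free survival) will be estimated using the Kaplan-Meier method for each patient cohort". No other method is stated for transformation.

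Transformation is a named secondary objective in Section 1.0 ("Overall response rate, survival, transformation to AML, transfusion independence"). Section 2.4 words it as a rate: "Secondary endpoints are overall response rate, rates of survival and transformation to AML, and toxicity profile".

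Section 7.0 defines the response categories but not AML transformation. No section gives the event, its time origin, its censoring rule or the handling of death without AML, and competing risks are not mentioned.

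Section 6.0 limits follow-up after treatment: "patients will be observed for survival only when off active treatment".

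**The concern.** Death without AML rules out later transformation, so it is a competing event and not ordinary censoring. The protocol recognises that such deaths occur. Section 2.1 says: "Patients die either from complications associated with cytopenias (infections and bleeding) or transformation to AML". It also puts median survival in intermediate-2 and high-risk disease at 0.4 to 1.2 years.

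If the event is AML alone, a Kaplan-Meier analysis censors these deaths. The curve then describes a setting in which nobody dies before transforming, and its complement is at or above the proportion who actually transform. A reader who takes it as the transformation rate promised in Section 2.4 would be misled.

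If the event is AML or death, Kaplan-Meier is a proper estimator of AML-free survival, but the transformation rate is left with no planned time-to-event estimator. The text needs repair on either reading.

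**Working it through.** **Which reading is natural.** Section 9.0 lists time to AML transformation apart from overall survival and event-free survival. Sections 1.0 and 2.4 list transformation apart from survival. The only composite wording is in Section 2.2 and describes a cited azacitidine trial: "The median time to leukemic transformation or death was 21 months on treatment and 13 months on observation". AML alone is therefore the likelier meaning, but the plan does not state it.

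**The inequality.** At each AML time u, let d(u) be the number transforming and n(u) the number at risk.

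- 1 − KM(t) = Σ S_AML(u−) · d(u)/n(u), where S_AML falls only at AML events.
- Cumulative incidence(t) = Σ S_all(u−) · d(u)/n(u), where S_all falls at AML events and at deaths without AML.

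Since S_AML ≥ S_all throughout, 1 − KM is at or above the cumulative incidence from the same data. They are equal up to t if no death without AML precedes an AML event counted by t.

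**Size.** The plan gives no target, event count or rate for this endpoint, so there is no figure to reproduce. What follows is an illustration. The inputs are:

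- m, median AML-free survival: 21 and 13 months (Section 2.2, azacitidine trial, treatment and observation arms); 15 and 12 months (Section 2.2, "Table 2. Decitabine - response rate in MDS by risk group", median survival in the intermediate-2 and high rows). The latter two are overall survival, an upper limit for AML-free survival.
- s, share of first events that are AML: 10% to 70%, from Section 2.1 ("MDS may evolve into acute myeloid leukemia (AML) in 10% to 70% of patients"). This covers all MDS, so it is only a rough guide.
- t: 24 months, matching the two-year treatment maximum in Section 4.1, and 12 months.
- Assumed: constant hazards and complete recording of AML.

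With h = ln 2 / m:

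- 1 − KM(t) = 1 − exp(−s·h·t)
- cumulative incidence(t) = s·(1 − exp(−h·t))

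Worked case, m = 15, s = 0.3, t = 24: h = 0.0462. Then 1 − KM = 1 − exp(−0.3 × 0.0462 × 24) = 28.3%, and the cumulative incidence = 0.3 × (1 − exp(−0.0462 × 24)) = 0.3 × 67.0% = 20.1%. The gap is 8.2 points.

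Gap in percentage points at 24 months:

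| m (months) | s=0.1 | 0.2 | 0.3 | 0.4 | 0.5 | 0.6 | 0.7 |
|---|---|---|---|---|---|---|---|
| 12 | 5.4 | 9.2 | 11.5 | 12.6 | 12.5 | 11.5 | 9.6 |
| 13 | 4.8 | 8.1 | 10.2 | 11.2 | 11.2 | 10.3 | 8.6 |
| 15 | 3.8 | 6.5 | 8.2 | 9.0 | 9.1 | 8.4 | 7.1 |
| 21 | 2.1 | 3.7 | 4.7 | 5.3 | 5.3 | 5.0 | 4.3 |

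The smallest gap is 7.6% against 5.5% (m = 21, s = 0.1). In the table the largest is 42.6% against 30.0% (m = 12, s = 0.4); a finer grid peaks at 12.7 points near s = 0.44. At 12 months the same inputs give 0.6 to 4.3 points.

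**Simulation.** In 3,000 simulated trials of 100 patients (m = 15, s = 0.3), 1 − KM at 24 months exceeded the Aalen-Johansen estimate every time. The means were 28.3% and 20.1%, and the smallest gap was 1.7 points.

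**Composite reading.** In the same case, one minus Kaplan-Meier for AML or death is 67.0% at 24 months, against a transformation incidence of 20.1%.

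**Recording of AML.** After treatment Section 6.0 follows survival only. Section 10.0 captures serious adverse events to 30 days after the last dose and then only treatment-related ones, so safety reporting does not clearly fill the gap. As a sensitivity check, let follow-up for AML stop at the end of treatment, with an assumed mean of 8 months on treatment and an AML hazard four times higher afterwards. The true 24-month incidence is then 43.4%, while the on-treatment 1 − KM has a target of 28.3% (25.6% in the run, where few patients remain at risk by 24 months). With an unchanged hazard the true incidence is about 20%, below the same target. The net error can go either way.

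**The case against.** The plan does not say that deaths will be censored or that one minus Kaplan-Meier will be reported as the proportion transforming. The rate in Section 2.4 could be given as a simple proportion, and the composite reading cannot be excluded. This stands as a caution: the firm fact is the missing definition, and the bias follows only on the likelier reading. No reading, however, makes the sentence in Section 9.0 an estimator of the transformation rate.

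Missed AML off treatment may matter more than the choice of estimator. In the fourfold-hazard example, changing only the estimator would move an already low figure further down. This also stands, and is why the fix covers data collection as well.

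The range of 2 to 13 points depends on the medians chosen. The azacitidine trial had only 67% advanced-stage disease. The medians in Section 2.1 for the target risk groups are 4.8 to 14.4 months (0.4 and 1.2 years × 12). The same formula gives about 20 to 36 points at 4.8 months and 4 to 10 at 14.4. Thirteen points is therefore not an upper bound, although those medians come from background natural history.

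Finally, no test, target or stopping rule uses this endpoint, and the gap is comparable to sampling error. In the central case the 95% half-width at n = 100 is 1.96 × √(0.201 × 0.799/100) = 7.9 points, against a gap of 8.2. That limits the importance, but the gap is systematic and the interval around the curve would not reveal it.

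**Conclusion.** The concern holds. Section 9.0 names Kaplan-Meier as the sole method for an undefined endpoint in a disease where death without the event is expected. On the AML-only reading, 1 − KM is at or above the cumulative incidence from the same data. That statement is exact; its size is not known.

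The illustrated excess of about 2 to 13 points at 24 months rests on constant hazards, full recording of AML, medians of 12 to 21 months and an AML share of 10% to 70%. Because AML after treatment may go unrecorded, the direction of error in the figure finally reported is not established.

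The matter should be corrected, but it is confined to a descriptive secondary endpoint. The CR analysis, sample size and stopping rules are unaffected.

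**What to change.** In the Statistical Analysis Plan of Section 9.0:

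- Define the event as transformation to AML, with its criterion and time origin.
- Estimate it by the cumulative incidence function (Aalen-Johansen), with death without AML as a competing event.
- Keep Kaplan-Meier for overall survival, event-free survival and, if wanted, a separately named AML-free survival counting AML or death.

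In Section 6.0, record AML status and date at the calls already scheduled 30 days after the last dose and every 2 months thereafter.

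The cost is one or two sentences in the plan and one added question per call. Confirming a date may sometimes need outside records. Dates not collected at the time may be hard to recover later, so the change is best made early.

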10.0 Reporting Requirements

Serious adverse events (SAEs) considered associated with therapy should be reported to the Principal Investigator [[[name]](#), M.D., [contact]] within 24 hours of observing or learning of the event. All AEs should be reported to the research nurse. The principal investigator, in turn, will be responsible for reporting the event to the IRB, FDA, and the SGI-110 manufacturer (Astex Pharmaceuticals, Inc.) as applicable in compliance with regulatory and institutional requirements. Adverse events will be graded using CTCAE version 4.03 (Appendix D)

Serious and unexpected adverse events will be reported according to MDACC guidelines. (Appendix C entitled "Leukemia Specific AE Recording Guidelines (09/2009)-Leukemia specific Adverse Event Recording and Reporting Guidelines". These events will be reported to the study chairman, who in turn will notify the Clinical Research Compliance office and the MDACC IRB. The Clinical Research Compliance Office will be responsible to notify the FDA according to 21CFR312.32.

- The investigator or physician designee is responsible for verifying and providing source documentation for all adverse events and assigning the attribution for each event for all subjects enrolled on the trial.
- Grade 3 or 4 related and/or unexpected adverse events and protocol specific data will be entered into PDMS/CORe. PDMS/CORe will be used as the electronic case report form for this protocol.

SERIOUS ADVERSE EVENT REPORTING FOR MD ANDERSON – IND SPONSORED PROTOCOLS

Serious Adverse Event Reporting (SAE)

An adverse event or suspected adverse reaction is considered "serious" if, in the view of either the investigator or the sponsor, it results in any of the following outcomes:

- Death
- A life-threatening adverse drug experience – any adverse experience that places the patient, in the view of the initial reporter, at immediate risk of death from the adverse experience as it occurred. It does not include an adverse experience that, had it occurred in a more severe form, might have caused death.
- Inpatient hospitalization or prolongation of existing hospitalization
- A persistent or significant incapacity or substantial disruption of the ability to conduct normal life functions.
- A congenital anomaly/birth defect.

Important medical events that may not result in death, be life-threatening, or require hospitalization may be considered a serious adverse drug experience when, based upon appropriate medical judgment, they may jeopardize the patient or subject and may require medical or surgical intervention to prevent one of the outcomes listed in this definition. Examples of such medical events include allergic bronchospasm requiring intensive treatment in an emergency room or at home, blood dyscrasias or convulsions that do not result in inpatient hospitalization, or the development of drug dependency or drug abuse (21 CFR 312.32).

- **Important medical events as defined above, may also be considered serious adverse events. Any important medical event can and should be reported as an SAE if deemed appropriate by the Principal Investigator or the IND Sponsor, IND Office.**
- All events occurring during the conduct of a protocol and meeting the definition of a SAE must be reported to the IRB in accordance with the timeframes and procedures outlined in "The University of Texas M. D. Anderson Cancer Center Institutional Review Board Policy for Investigators on Reporting Unanticipated Adverse Events for Drugs and Devices". Unless stated otherwise in the protocol, all SAEs, expected or unexpected, must be reported to the IND Office, regardless of attribution (within 5 working days of knowledge of the event).
- **All life-threatening or fatal events**, that are unexpected, and related to the study drug, must have a written report submitted within **24 hours** (next working day) of knowledge of the event to the Safety Project Manager in the IND Office.

- Unless otherwise noted, the electronic SAE application (eSAE) will be utilized for safety reporting to the IND Office and MDACC IRB.
- Serious adverse events will be captured from the time of the first protocol-specific intervention, until 30 days after the last dose of drug, unless the participant withdraws consent. Serious adverse events must be followed until clinical recovery is complete and laboratory tests have returned to baseline, progression of the event has stabilized, or there has been acceptable resolution of the event.
- Additionally, any serious adverse events that occur after the 30 day time period that are related to the study treatment must be reported to the IND Office. This may include the development of a secondary malignancy.

Reporting to FDA

Serious adverse events will be forwarded to FDA by the IND Sponsor (Safety Project Manager IND Office) according to 21 CFR 312.32.

It is the responsibility of the PI and the research team to ensure serious adverse events are reported according to the Code of Federal Regulations, Good Clinical Practices, the protocol guidelines, the sponsor's guidelines, and Institutional Review Board policy.

Investigator Communication with Supporting Companies:

Reporting to Astex Drug Safety.

The Investigator will notify Astex, as designated holder of the global safety database, of any Serious Adverse Event (SAE), pregnancy, or infant exposure, including those events reported to the Investigator by his/her Investigators, whether related to Study Drug or not, within twenty-four (24) hours of being made aware of the SAE. Such notification will be provided to Astex by faxing the information contained in the exemplar Serious Adverse Event Report Form, which is appended to the Protocol, to the Astex Drug Safety Department:

Astex Drug Safety SAE Reporting Fax Number

Local [contact]

North America Toll-Free [contact]

A copy of the correspondence sent to the FDA [or other controlling regulatory authority] shall be sent within twenty-four (24) hours to Astex Regulatory Affairs by email or fax:

Astex Regulatory Affairs email: [contact]

Astex Regulatory Affairs [contact]

Disputed SAEs. Even if the Investigator decides not to report an event, Astex may make its own determination that it is a reportable Serious Adverse Event, and may report it.

11. References

- 1) Cheson BD, et al. Report of an international working group to standardize response criteria in myelodysplastic syndromes. *Blood* 2000; 96: 3671-3674.
- 3) Bennett JM, et al. Proposals for the classification of the myelodysplastic syndromes. *Br J Haematol* 1982; 51: 2499-2509.
- 5) Greenberg P, et al. International scoring system for evaluating prognosis in myelodysplastic syndromes. *Blood* 1997; 89: 2079-2088.
- 6) Silverman LR et al. Randomized controlled trial of azacitidine in patients with myelodysplastic syndrome: a study of the Cancer and Leukemia Group B. *J Clin Oncol* 2002; 20: 2429-2440.
